The participant incentives are not intended to be an enticement to smoke hookah within the café, but rather as compensation for time needed to complete the surveys and eCO monitoring, which we anticipate will take up to 20 minutes at each time point. Participants will only be eligible if they indicate they are planning to smoke hookah in the café. We will not recruit people to come to the café, but rather recruit café customers to participants in the study. Participants will be instructed to behave as they normally would in the café. The incentive will not be able to be used in the café.

Figure 1. Table Sign

Pilot/Soft Launch

We will conduct a pilot/soft launch with a single hookah café to assess feasibility of the protocol and to make changes, if required, before conducting the full trial. Any changes to protocol and/or measures will be submitted as amendments before conducting the remainder of the trial. If no changes are made as a result of the soft launch, this café will be included in the final study sample. If significant changes are made as a result of the soft launch, we will conduct the study with up to 25 additional cafés and the data from the soft launch café will not be included in the final dataset. We will implement both text-only and pictorial warnings on different nights at the pilot café to fully test the two versions of the intervention signs, in addition to the control arm.

Outcome Measure(s)

Primary Outcome

Change in Expired Carbon Monoxide from baseline to follow-up. We will use eCO, an objective, biological marker of waterpipe tobacco consumption. There is a linear relationship between waterpipe tobacco smoking intensity and carboxyhemoglobin concentration, and eCO is strongly correlated with several topography measures of waterpipe smoking. Carbon monoxide has a half-life of 3-4 hours and is influenced by other forms of combustible tobacco; therefore, the primary outcome will be the change in eCO from before entry to after café exit, known as eCO boost. We will also record the percentage of carboxyhemoglobin concentration measured by the CO monitor.

Secondary Outcome(s)

None

Other Outcomes

Behavioral intentions. Participants will be asked at Time 2 three items assessing their expected hookah smoking within the next month. Items will be averaged to create a composite score of intent to continue the behavior within the next month.

1. How interested are you in smoking tobacco in a hookah in the next month?

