2. How likely are you to smoke tobacco in a hookah in the next month?
3. How much do you plan to smoke tobacco in a hookah in the next month?

Response Options: (1) Not at all, (2) A little, (3) Somewhat, (4) Very, (5) Extremely

Quit motivation. One item to measure participants' motivation to quit smoking hookah, rated on a 1-10 scale of Not at all motivated – Extremely motivated. This item is asked only of those who did not smoke for the first time tonight (by self-report).

Hookah use behaviors. Participants will be asked a variety of items to assess their hookah smoking behaviors within the café. Items will be scored individually.

1. Did you smoke hookah in this café/lounge/bar today? (1) Yes, (2) No
2. (If no) Why didn't you smoke hookah in this café/lounge/bar today? Free text response
3. (If yes) Compared to a typical night, how much did you smoke? (1) Less hookah than usual, (2) About the same amount of hookah as usual, (3) More hookah than usual, (4) This was my first time smoking hookah
4. (If less) Why did you smoke less than usual? Free text response
5. (If more) Why did you smoke more than usual? Free text response

Subjective experiences of smoking hookah. Eight items of the Satisfaction subscale of the Product Evaluation Scale¹² will be used to assess participants' subjective experiences of smoking hookah. Items scores will be averaged across the subscale.

1. Was it satisfying?
2. Did it taste good?
3. Did you enjoy the sensations in your mouth?
4. Did you enjoy it?

5. Did it make you dizzy?
6. Did it make you nauseous?
7. Was it too much nicotine?
8. Were there bothersome side effects?

Response options: (1) Not at all – (7) Extremely

Knowledge. Four items to measure the participants' knowledge of the health harms presented by the four selected warnings used in the study, although participants will be exposed to none (Control) or only one (Intervention) during their participation.

Beliefs. Four items to assess the participants' belief that the health effects named by the four selected warnings will affect them personally.

Warning recall. One Y/N item and one free-text follow-up to assess participants' recall of warning messages shown (if any) during participation.

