of individuals within study arm within cafés. We let eCO_{ijk} represent the outcome measurement for individual k within study arm j within cluster (café) I , assumed continuous and normally distributed. The model will include a fixed effect for study arm (intervention or control) and random cluster and cluster-arm effects. Models will adjust for individual-level sociodemographics and tobacco use at baseline. In secondary analyses, we will examine the impact of sociability of waterpipe behavior by adjusting models for the number of people with whom the individual is smoking in the café. Secondary analyses will examine the impact of text versus pictorial warnings. These hierarchical models will be fit using PROC MIXED in SAS. Because the intervention effect is estimated within clusters, it is also adequate to model fixed cluster effects but retain random cluster-arm effects. Turner (2007) demonstrated through simulation that these two models perform similarly with 18 clusters with slight differences depending on the degree of correlation. We will examine both approaches as a sensitivity analysis.²² Using the same HLM modeling approach, we will perform analyses on secondary outcomes shown in Table 5.

Human Subjects Protection

Overview

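### The Satisfaction score averages four favourable and four aversive items on one scale with no scoring direction, so as written it does not measure satisfaction and can hide an arm difference

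*Combined protocol and SAP*

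**What the plan says.** In the combined protocol and SAP, under Other Outcomes, Subjective experiences of smoking hookah, the instrument is described as "Eight items of the Satisfaction subscale of the Product Evaluation Scale". Items 1-4 ask about favourable experience: satisfaction, taste, sensations in the mouth and enjoyment. The first is "Was it satisfying". Items 5-8 ask about aversive experience: dizziness, nausea, excess nicotine and side effects. The last is "Were there bothersome side effects". All eight share one response scale, from 1 for not at all to 7 for extremely.

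The scoring rule is a single sentence: "Items scores will be averaged across the subscale". Neither this section nor the Analytical Plan mentions reverse scoring, the meaning of a high score, or a split into two scores.

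The only other composite with listed items is Behavioral intentions ("Items will be averaged to create a composite score of intent to continue the behavior within the next month"), and its three items all point the same way. On analysis, the Analytical Plan says that with the same hierarchical model "we will perform analyses on secondary outcomes shown in Table 5". Table 5 is not in the available text.

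**The concern.** A high answer to items 1-4 means a better experience, and a high answer to items 5-8 means a worse one. A plain average of the two halves has no clear meaning: its maximum of 7.0 needs full enjoyment together with maximal dizziness, nausea, excess nicotine and side effects.

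The documents do not say which way a warning should move items 5-8. Reported side effects could rise if the warning makes people attend to them, or fall if people smoke less. Depending on the direction, the averaged score can shrink an effect on enjoyment, cancel it, reverse its sign, or show an effect when enjoyment has not changed. A reader given only the single score could not tell these cases apart.

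The outcome is not incidental to the trial's question. The stated objective covers behavioural antecedents as well as eCO. The laboratory study of warnings that the Analytical Plan uses as its benchmark is listed in the References under a title that reports reduced smoking satisfaction. Readers will want to compare the two results, and this score would not support that.

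**Working it through.** The plan gives no figure for this outcome, so there is none to reproduce. The check applies the scoring rule as written.

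**Inputs from the protocol.** Eight items, four favourable and four aversive; the same 1-7 scale for all; a plain average.

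**Notation.** P is the mean of items 1-4 and A the mean of items 5-8. dP and dA are the arm differences (intervention minus control) in these means.

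- As written: score = (4P + 4A)/8 = (P + A)/2, so the arm difference is (dP + dA)/2.
- With items 5-8 reversed as 8 - x: score = (P + 8 - A)/2, so the arm difference is (dP - dA)/2.

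**Individual scores.**

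- Full enjoyment, no side effects (7,7,7,7,1,1,1,1): (28 + 4)/8 = 4.0.
- No enjoyment, maximal side effects (1,1,1,1,7,7,7,7): (4 + 28)/8 = 4.0.
- Sevens throughout: 7.0.

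**Arm differences.** The shifts are illustrative.

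| dP | dA | As written | Reverse-coded |
|---|---|---|---|
| -1 | +1 | 0 | -1.00 |
| -1 | +0.5 | -0.25 | -0.75 |
| -1 | 0 | -0.50 | -0.50 |
| -1 | -0.5 | -0.75 | -0.25 |
| -1 | -1 | -1.00 | 0 |
| 0 | -1 | -0.50 | +0.50 |
| -0.5 | +1 | +0.25 | -0.75 |

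As written, the first row hides a real loss of enjoyment, the sixth shows a loss that did not occur, and the last has the wrong sign for enjoyment. The fifth row shows that reverse coding has its own blind spot.

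**Cost in precision when only enjoyment changes (dA = 0).** Assume equal SDs s for P and A, and a correlation rho between them of -0.3 to +0.3; the documents give neither. The SD of the written score is s × sqrt((1 + rho)/2). Its standardised effect, relative to items 1-4 alone, is 0.5/sqrt((1 + rho)/2):

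- rho = -0.3: 0.5/sqrt(0.35) = 0.85
- rho = 0: 0.5/sqrt(0.5) = 0.71
- rho = +0.3: 0.5/sqrt(0.65) = 0.62

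The sample multiplier needed to match the power of items 1-4 is the inverse square, 2(1 + rho): 1.4, 2.0 and 2.6. This takes the same intraclass and inter-period correlations for both scores.

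**Illustrative power.** Take the plan's 20 cafés and 15 patrons per arm, its r of 0.10 or 0.30 and h = r/2. Assume a half-score SD of 1.5, rho = -0.3 and two-sided alpha of 0.05. The variance factor 1 + 14r - 15h is 1.65 at r = 0.10 and 2.95 at r = 0.30. The standard error is sqrt(2 × variance × factor/300). For dP = -0.5 and dA = +0.25, the written score has difference -0.125 and variance 2.25 × 1.4/4 = 0.7875.

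- r = 0.10: power is 27% as written and 89% for items 1-4 alone.
- r = 0.30: power is 17% as written and 66% for items 1-4 alone.

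With dA = +0.5 the written difference is 0 and power equals alpha, 5%.

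**The case against.** **The scoring may be defined elsewhere.** The protocol names a published scale and cites its validation paper, and the items as administered are in the Time 2 Survey, which is listed in the Appendix but not reproduced. Protocols often leave item direction to the instrument. This stands as a limit on the claim: the analysts may intend something other than what is written. But the protocol does not say that it follows the published scoring. It states its own rule, and that rule gives the wrong result.

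**The stakes are low.** This is one of many Other Outcomes, with no hypothesis or power claim attached. The item responses are kept, so the score can be rebuilt. A formal arm comparison is only inferred, because the protocol lists no secondary outcomes while the Analytical Plan refers to secondary outcomes in Table 5. All of this is fair and limits the severity. It does not make the rule usable, and choosing a score after seeing the data would make the choice data-dependent.

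**The precision loss is not specific to missing direction.** This is correct. When only enjoyment changes, a reverse-coded average loses the same range of efficiency, with the correlations mirrored. The multiplier compares the written score with items 1-4 alone, and shows the cost of any eight-item composite in that case.

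**The contrast with other items is weak.** The protocol does give another rule for the hookah use items ("Items will be scored individually"). Those items are categorical or free text and could not sensibly be averaged, so the contrast says little about intent, and the conclusion does not rest on it.

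**Two scores are a preference.** A net-experience score is a coherent quantity, and nothing in the documents shows that items 5-8 form one scale. But a net score answers a different question from satisfaction, and it too can cancel.

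**Conclusion.** The concern holds for the rule as written. The average does not rank patrons by satisfaction: opposite extremes both score 4.0. An arm difference in enjoyment can be halved, cancelled or reversed, and a change in side effects alone can appear as a change in satisfaction.

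The scoring arithmetic needs no assumption beyond the listed items, the common 1-7 scale and the stated average. How large the distortion would be in this trial depends on how items 5-8 move, which the documents do not say. The 1.4 to 2.6 multiplier and the power figures also rest on assumed SDs and correlations. The scoring should be corrected before analysis. The consequence is confined to one Other Outcome.

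**What to change.** Before analysis, replace the single average with two scores, each on the 1-7 scale and each with a stated direction:

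- **Satisfaction:** mean of items 1-4, higher meaning a better experience.
- **Aversive effects:** mean of items 5-8, higher meaning a worse experience.

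Fit the same hierarchical model to each and report both. Do not rely on one reverse-coded average in their place.

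The cost is one sentence in the plan, one line of scoring code and one more exploratory outcome to report. Item responses already collected are enough; data collection, the primary analysis and the sample size do not change.

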The goal of the overall grant is to develop warnings to promote greater understanding of harms and to reduce WTS behavior among young adults. We have used a systematic, evidence-driven, rigorous approach to develop waterpipe warnings and test these newly developed warnings in two contexts: (1) on waterpipe tobacco packaging; and (2) in an ecologically valid waterpipe café setting. In Aim 1, we developed text and pictorial waterpipe tobacco warnings to effectively communicate a broad range of health harms. We first developed 30 text warnings based on three themes: acute health harms, chronic health harms, and correcting misperceptions. We tested these warnings in a national survey to determine the five most effective text warnings (IRB00062703). We then selected three illustrative images of the health effects presented by the warnings for each of these warnings, plus the federally mandated nicotine warning. We conducted an experiment to determine the most effective image for each of the six warning messages (IRB00080199). In Aim 2 (IRB00091946), we compared the effects of pictorial warnings versus the text-only warnings and a no-warning control placed on fictional packaging on WTS intentions.

Warning placement on packaging and at the point-of-sale is typically the result of legal mandates. In order to approximate the impact of a legal mandate to require health warnings at the point-of-sale, we will partner with places that sell waterpipe tobacco for use onsite. These places may be cafés, restaurants, lounges, bar, etc. (herein referred to as “hookah cafés”). Conducting an experiment where hookah café customers are exposed to waterpipe warnings will allow us to test the impact of the warnings on actual behavior, in the absence of legal mandates. In this experiment (Aim 3), we will conduct a cluster randomized crossover trial with up to 32 hookah cafés in Atlanta, GA (1 pilot and 31 trial cafés). We plan to overenroll cafés to account for dropout/early termination. The goal is at least 20 cafés with 15 participants per arm. Each café will serve as its own comparison as it cycles through the two trial arms: intervention (text warning) and control (no warning). The pictorial warning condition was removed in July 2024 after consultation with E&W and NCI regarding unwillingness of cafés to allow placement of pictorial warning signs. We will randomly select one of four health warning messages from Aim 2 to be displayed in each of

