the partner café. However, each café will only have one warning displayed on its premises for the duration of its participation in the intervention arm.

Objective(s)

1. To determine the effect of warnings on hookah smoking behavior, measured with an objective biomarker of consumption (expired carbon monoxide), and behavioral antecedents.

Roles

Wake Forest Baptist Health

Wake Forest's role in this study will be to develop the protocol and data collection instruments, create the study stimuli, program all online data collection tools, train data collectors hired by Ewald & Wasserman, monitor data collection, conduct all analyses, and lead dissemination of results.

University of North Carolina at Chapel Hill

[name] will assist in developing data collection instruments and interpreting the results of analyses on final data.

Boston University

[name] will assist in developing data collection instruments and interpreting the results of analyses on final data.

Ewald & Wasserman Research Consultants, L32

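### Knowledge and Beliefs: four items each, one warning per café and no scoring rule; averaging the items, or pooling each item over all cafés, would dilute a message-specific effect

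*Combined protocol and SAP*

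**What the plan says.** All references are to the combined protocol and SAP.

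- **Items.** Under Outcome Measure(s), Other Outcomes, four items measure "knowledge of the health harms presented by the four selected warnings used in the study", and four more measure the "belief that the health effects named by the four selected warnings will affect them personally".
- **Exposure.** The opening section says "We will randomly select one of four health warning messages from Aim 2" for each partner café, and that "each café will only have one warning displayed on its premises for the duration of its participation in the intervention arm". The Knowledge paragraph accepts the consequence: "participants will be exposed to none (Control) or only one (Intervention) during their participation".
- **Scoring.** None is given for Knowledge or Beliefs. Other multi-item outcomes do have a rule. For intentions it is "Items will be averaged to create a composite score of intent to continue the behavior within the next month"; the subjective-experience items are also averaged, and the hookah use items are scored one by one.
- **Model.** The Analytical Plan states: "The model will include a fixed effect for study arm (intervention or control". It adds random café and café-arm effects and individual-level covariates. It names no term for the message displayed.
- **Status.** Both outcomes sit under Other Outcomes, and the secondary-outcome entry reads none. The Analytical Plan extends the model to secondary outcomes in a Table 5 that is not in the text available for review.

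**The concern.** The measurement covers four harms and each café's intervention covers one. The protocol elsewhere uses two scoring conventions, averaging and item by item. Under averaging, one targeted item is mixed with three untargeted ones. Under item-by-item comparison over all cafés, only about a quarter of intervention cafés (about 5 of 20) displayed the harm that the item asks about. In both cases, most of what enters the arm contrast is not aimed at by the warning that was shown.

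The overall grant aims at better understanding of harms as well as less smoking, and these two outcomes are the closest measures of understanding. If a warning teaches its own harm and little else, a diluted score could make it look as if the warning taught nothing. Leaving the choice open until the data are seen also leaves room to pick the scoring after the fact.

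**Working it through.** **1. The plan's own figure.** Inputs from the Analytical Plan: k = 20 cafés, m = 15 per arm, SD = 30 ppm, r = 0.10 or 0.30, h = r/2, power 80%. Alpha is not stated; two-sided 5% is assumed.

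MDD = (1.960 + 0.842) × 30 × √(2 × [1 + (m − 1)r − mh] / (km))

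- r = 0.10: bracket = 1 + 1.40 − 0.75 = 1.65; √(3.30/300) = 0.1049; MDD = 8.81 ppm.
- r = 0.30: bracket = 1 + 4.20 − 2.25 = 2.95; √(5.90/300) = 0.1402; MDD = 11.79 ppm.

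The plan gives 8.81 and 11.78, so the variance formula is reproduced. (One-sided 5% would give 7.82 and 10.46.)

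**2. Size of the dilution.** Let the displayed harm's item shift by d item-SDs and the other three by qd, where q is the spillover fraction. Let c be the inter-item correlation. The documents give none of d, q or c.

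- Mean of four items, raw shift: d(1 + 3q)/4. With q = 0 this is d/4; with q = 0.25 it is 0.44d; with q = 0.5 it is 0.625d.
- SD of the mean: √((1 + 3c)/4). With q = 0 the standardised effect is therefore d / (2√(1 + 3c)), a loss of 2.0-fold at c = 0, 2.8 at c = 0.3, 3.2 at c = 0.5 and 4.0 at c = 1. A sum score avoids the raw shrinkage but has the same standardised loss.
- One item compared over all cafés, with equal message shares and q = 0: d/4, raw and standardised.

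**3. Power.** Assumptions: d = 0.4; the eCO values of r and h apply to the items and to their mean; continuous scores; noncentral t on 19 df, two-sided 5%. With SD = 1, the SE is 0.105 (r = 0.10) or 0.140 (r = 0.30). For the matched item the noncentrality is 0.4/0.105 = 3.81 or 0.4/0.140 = 2.85. Ranges for the mean run from c = 0.5 to c = 0.3.

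| Outcome | r = 0.10 | r = 0.30 |
|---|---|---|
| Item matching the café's message | 95% | 77% |
| One item over all cafés, q = 0 | 15% | 10% |
| Four-item mean, q = 0 | 21–26% | 14–17% |
| Four-item mean, q = 0.25 | 52–63% | 32–40% |
| Four-item mean, q = 0.5 | 82–91% | 57–69% |

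Testing each item only in the five or so cafés that showed its message does not rescue the analysis: on 4 df, power is 31% at r = 0.10.

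**The case against.** The strongest reply is that no diluted analysis is planned. These are Other Outcomes without a scoring rule, the model is written out for eCO, and its extension is to secondary outcomes in a table that cannot be read here. That is right. A reader might infer that the protocol commits itself to a four-item composite or a pooled item; the documents do not say so. What stands is that the two scoring conventions used elsewhere in the protocol would both dilute, and that nothing in the text points to matching.

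A second reply is that the model does not rule out the message. The plan chooses hierarchical modelling partly because it can carry café-level covariates, and the displayed message is one. This also stands: a matched score runs in the stated model unchanged. The gap lies in the outcome definition.

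A third reply is spillover. A warning about lung damage may raise concern about the heart as well. The table shows how much this matters: at 50% spillover and r = 0.10 the mean loses little against the matched item. The documents give no basis for choosing q, so a prediction that real effects would be reported as null holds only when spillover is small.

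Finally, a reader might take knowledge and beliefs to be named in the objective. The objective refers to antecedents of behaviour in general and names neither.

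**Conclusion.** The point holds as a gap in outcome definition with a clearly better option available. With no spillover and equal message shares, an effect on the displayed harm falls to about one quarter on the raw scale, whether the items are averaged or a single item is pooled over all cafés. A fourfold loss should not be read as general: for a standardised four-item composite it is 2- to 4-fold, and spillover reduces it further. At d = 0.4 and r = 0.10, power falls from about 95% to 15–26% without spillover. At r = 0.30 the matched item itself has only 77%.

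These powers rest on an assumed effect size, on correlations borrowed from eCO, and on continuous scores. The protocol gives no response scale for these items, and a binary scale would change the figures. The primary eCO outcome and the sample size are not affected.

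**What to change.** Pre-specify, before analysis, as the main contrast for Knowledge and for Beliefs the item that matches the message assigned to the café. Compare that same item between the café's intervention and control periods in the same hierarchical model, with a term for which message (and so which item) is used. In the sensitivity model with fixed café effects, that term is absorbed by the café.

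Report the three non-displayed items separately as a spillover analysis. They should not be labelled a negative control, because a real effect that generalises across harms would then be read as bias.

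The cost is wording in the analysis plan. As described, all four items are asked in both arms and each café's message is known, so no further data, cafés or participants are needed. There is one small downside: the outcome combines four different items across cafés, so the estimate is an average of four message-specific effects. The within-café comparison removes differences in baseline level between items. Balancing messages across cafés would be a change to the random selection procedure and is not needed for this fix.
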